# 4.0 Study Design

This is a single cohort phase I study to determine the safety of plerixafor mobilization and apheresis in SCD patients. With amendment C, this protocol becomes a multi-institute study with the inclusion of St. Jude Children's Research hospital as a participating site.

# At Participating Site:

For St. Jude Children's Research Hospital, see Appendix II for site-specific protocol changes and activities.

# 5.0 Eligibility Assessment

SCD patients who are age 18 or greater and: (a) are to enroll on a clinical trial with curative intent in which a backup bone marrow harvest is required (e.g. allogeneic HSCT), or (b) are willing to donate hematopoietic stem cell collection for future gene therapy/gene editing study, are eligible for study entry. Patients who are not receiving long-term transfusion therapy will receive prophylactic red cell exchange prior to plerixafor administration to target the fraction of hemoglobin S <30% to reduce the incidence of vaso-occlusive crisis and other sickle related complications. Patients on red cell transfusions can either maintain on transfusions or undergo a modified exchange (e.g. mini-exchange) prior to plerixafor. Hydroxyurea treatment should be stopped at least 2 weeks before mobilization, since the washout period is important for bone marrow recovery to reduce the myelosuppressive effects of hydroxyurea.

Plerixafor may have adverse effects on a fetus *in utero*. Furthermore, it is not known if Plerixafor has transient adverse effects on the composition of sperm.

For this trial, male subjects will be considered of non-reproductive potential if they have azoospermia (whether due to having had a vasectomy or due to an underlying medical condition).

Female subjects will be considered of non-reproductive potential if they are either:

postmenopausal (defined as at least 12 months with no menses without an alternative medical cause; in women < 45 years of age a high follicle stimulating hormone (FSH) level in the postmenopausal range may be used to confirm a post-menopausal state in women not using hormonal contraception or hormonal replacement therapy. In the absence of 12 months of amenorrhea, a single FSH measurement is insufficient.);

OR

have had a hysterectomy and/or bilateral oophorectomy, bilateral salpingectomy or bilateral tubal ligation/occlusion, at least 6 weeks prior to screening;

OR

has a congenital or acquired condition that prevents childbearing.

Female and male subjects of reproductive potential must agree to avoid becoming pregnant or impregnating a partner, respectively, while receiving study drug by complying with one of the following contraception regimens if sexually active:

Single method (one of the following is acceptable):

- intrauterine device (IUD)
- vasectomy of a female subject's male partner
- contraceptive rod implanted into the skin

Combination method (requires use of two of the following):

- diaphragm with spermicide (cannot be used in conjunction with cervical cap/spermicide)
- cervical cap with spermicide (nulliparous women only)
- contraceptive sponge (nulliparous women only)
- male condom or female condom (cannot be used together)

• hormonal contraceptive: oral contraceptive pill (estrogen/progestin pill or progestin-only pill), contraceptive skin patch, vaginal contraceptive ring, or subcutaneous contraceptive injection

Subjects should be informed that taking the study medication may involve unknown risks to the fetus (unborn baby) if pregnancy were to occur during the study. All patients must agree to an effective method of contraception while on study treatment and for at least 3 months following Plerixafor treatment (including both female patients of child-bearing potential and male patients with partners of child-bearing potential). Effective birth control includes: a) birth control pills, depot progesterone, or an intrauterine device plus one barrier method, or b) two barrier methods.

Effective barrier methods are: male and female condoms, diaphragms, and spermicides (creams or gels that contain a chemical to kill sperm). For patients using a hormonal contraceptive method, information about any interaction of Plerixafor with hormonal contraceptives is not known. If there is any question that a subject of childbearing potential will not reliably comply with the requirements for contraception, that subject should not be entered into the study.

All patients will be evaluated first with a medical history and physical examination. Baseline laboratory tests include:

- complete blood count and differential
- hemoglobin analysis
- blood chemistry studies (electrolytes and liver and renal function tests)
- ABO blood typing
- serological tests for syphilis (RPR)
- hepatitis B and C (HBsAg, Anti-HCV)
- HIV (anti-HIV 1/2)
- HTLV-I/II (anti-HTLV-I/II)
- abdominal ultrasound (baseline)
- other relevant tests that investigators consider important to establish a complete medical history will be performed
- All female patients of childbearing age will be required to undergo a serum or urine pregnancy test.
- 5.1 Inclusion criteria:
  - **5.1.1.** SCD patients who are 18 or older, and (a) planned to enroll in an active allogeneic HSCT study where back-up autologous HSCs are needed; OR (b) are eligible for an allogeneic HSCT study [i.e. have the same disease severity as group (a), but no active allogeneic HSCT study is available], and are willing to donate autologous HSCs for a future gene therapy, gene editing, or allogeneic HSCT study.
  - **5.1.2.** Adequate renal function: serum/plasma creatinine <1.5 mg/dL.
  - **5.1.3.** Adequate liver function: direct bilirubin and ALT <5 times the upper limit of normal range.
  - **5.1.4.** Blood counts: WBC >3,000/mm3, granulocytes >1,000/mm3, hemoglobin>7.0g/dL, platelets>150,000/mm3.
  - **5.1.5.** Female patients of childbearing age should have a negative serum pregnancy test within one week of beginning plerixafor administration, have had a hysterectomy, post-menopausal, or absence of a menses for over a year.
  - **5.1.6.** Meets NIH Department of Transfusion Medicine (DTM) eligibility criteria for blood component donation for *in vitro* research use (negative serologic tests for syphilis, hepatitis B and C, HIV, and HTLV-1).
  - **5.1.7.** Ability to give informed consent to participate in the protocol.
  - **5.1.8** Female and male individuals of reproductive potential must agree to one of the contraceptive regimens stated above if sexually active
- **5.2** Exclusion criteria:

- **5.2.1.** Pregnancy. Female patients of childbearing age should have a negative serum pregnancy test within one week of beginning plerixafor administration, except those that have had a hysterectomy, post-menopausal, or an absence of a menses for over a year.
- **5.2.2.** Active viral, bacterial, fungal, or parasitic infection.
- **5.2.3.** History of cancer, excluding squamous carcinoma of the skin and cervical carcinoma in situ.
- **5.2.4.** Active and painful splenomegaly or splenomegaly (size greater than upper limit of normal) determined by ultrasound.
- **5.2.5.** Allergy to plerixafor.

## At Participating Site:

For St. Jude Children's Research Hospital, see Appendix II for site-specific protocol changes and activities.

## 6.0 Treatment Plan

## At NIH

- 6.1 Prophylactic red blood cell exchange or simple red cell transfusions will be given to patients prior to plerixafor administration targeting HbS <30% to reduce the incidence of vaso-occlusive crisis and other events that may be associated with high hemoglobin S levels. Hydroxyurea treatment should be stopped at least 2 weeks before mobilization, since the washout period is important for bone marrow recovery after myelosuppressive effects of hydroxyurea.
- 6.2 Patients undergoing HSC mobilization will be admitted on a telemetry medical unit. They will then receive a single-dose subcutaneous administration of plerixafor (Mozobil®) at 240 μg/kg. (If the CD34+ cell yields are not sufficient for a minimal target dose in each protocol, a second plerixafor administration can be performed at the same dose for mobilization and apheresis the following day.)
- **6.3** Patients will be monitored continuously by telemetry. Leukapheresis will start approximately 4-12 hours after plerixafor is given. Mononuclear cells will be collected using an automated cell separator or apheresis device. Whole blood is withdrawn from one venipuncture site at a rate of 60-80 mL/min and then conveyed to the separator. If IV access is inadequate, central lines will be inserted prior to apheresis. Leukapheresis will be performed by the Apheresis Unit under supervision of the medical staff of the Department of Transfusion Medicine at the NIH Clinical Center with periodic EKG monitoring, or in a nursing unit where continuous cardiac monitoring (telemetry) can start with plerixafor administration and through the apheresis procedure.
- 6.4 After successful blood withdrawal, blood is separated into cells and plasma by centrifugation. The light density mononuclear cells are collected into a component bag, and the remaining cells and plasma are re-infused into the patient via a second venipuncture site. Acid Citrate Dextrose formula A (ACD-A) is used as the anticoagulant at a whole blood to anticoagulant ratio of 13:1. Prophylactic intravenous calcium infusions are used in all procedures. Maximal extracorporeal blood volume during the procedure ranges from

300-400 mL. Sufficient volumes of blood will be processed to obtain target CD34+ cells of 2.0x10e6 CD34+ cells/kg (minimum of 1.5x10e6 cells/kg).

- **6.5** The harvested peripheral blood apheresis products will be cryopreserved using a controlled rate freezer. All excess cells beyond 2.0x10e6 CD34+ cells/kg will be available for immediate CD34+ cell selection and freezing for research testing cell culture, lentiviral transduction, gene editing, and xenotransplantation.
- 6.6 After successful mobilization and stem cell collection, patients will remain in the hospital for 1-3 days to monitor for side effects. The total inpatient duration is about 1 week. 3-10 days after discharge from hospital, patients will be evaluated in outpatient clinic. Laboratory and other testing will be obtained as clinically indicated.
- 6.7 Additional blood samples may be drawn before plerixafor administration, 2 hours after plerixafor, when starting apheresis, and at the end of apheresis to study CD3, CD34, and total nucleated cell counts. The total amount of blood to be drawn including the screening labs will adhere to the policy for adult patients.
- **6.8** Patients will complete this study 10 days after the last dose of plerixafor, and be taken off this protocol.

# At Participating Site:

For St. Jude Children's Research Hospital, see Appendix II for site-specific protocol changes and activities.

# 7.0 Sample Collection, Storage, and Biospecimen and Data Management Plan

# At NIH

7.1 Data management

The PI will be responsible for overseeing entry of data into a password-protected electronic system that complies with NIH security standards and NHLBI DIR policy, and for ensuring data accuracy, consistency and timeliness of entry. The PI, associate investigators, research nurses, and/or a contracted data manager will assist with the data management efforts. All human subject personally identifiable information (PII) eligibility and consent verification will be recorded in conformity with DIR policy. Primary and final analyzed data will have unique codes so that research data can be attributed to an individual human subject participant.

7.2 Intended use

Blood samples and data collected and stored for research purposes will be used to study alternative stem cell selection strategies and culture techniques. Research samples will be stored indefinitely in NIH freezers. Patient clinical data will be protected and tracked using standard operating procedures in the medical record department. The IRB will be notified if research samples are unintentionally destroyed or lost.

# 7.3 End of study procedures

Data will be stored in a password-protected database in conformity with NHLBI DIR policy or in a publicly accessible research repository until they are no longer of scientific value. Data may be destroyed only when permitted by the clinical director and approved by the IRB.

# 7.4 Loss or destruction of data

Should the research team become aware that a major breech in our plan to protect research subject confidentiality and trial data has occurred, the clinical director and IRB will be notified.

# 7.5 Data sharing and future use of data

Research data may be shared with qualified non-collaborator recipients following publication of the primary research results after removal of PII and IRB approval. Future research use of data not defined in the research protocol may occur only after IRB review and approval or an exemption from the NIH Office of Human Subjects Research Protections (OHSRP). Refusal of a research subject participant to permit future use of data--other than required in the protocol or by the FDA--will be honored. Limitations in data sharing and future use of data due to contractual obligations (e.g., CRADAs) or intellectual property proceedings (such as patent filings) will be honored.

# 7.6 Future use of biospecimens

After analyzing the biospecimens for primary research purposes as described in the protocol, remaining samples suitable for future research must be stored in manner that conforms with DIR policy (such as BSI) or in a publicly accessible research biospecimen repository following IRB or OHSRP approval. Biospecimens may be destroyed only when permitted by the clinical director and approved by the IRB.

Any future research use of biospecimens not defined in the protocol in which NHLBI investigators are engaged in research (e.g., they are undertaking research activities and hold the key that identifies research subjects) requires IRB review and approval. Coded biospecimens (NHLBI investigators hold the key that identifies research subjects) to be shared outside of NIH for future research use requires IRB review and approval (for research collaborations) or submission of a determination to OHSRP (for non-collaborative research), and an executed transfer agreement. Unlinked biospecimens (no key to identify research subjects exists) to be shared outside of NIH for future research use requires submission of a determination to OHSRP and an executed transfer agreement. There are a few types of biospecimens that do not require IRB or OHSRP approval for future research use outside of NIH, such as specimens from deceased individuals (refer to OHSRP SOP5, Appendix 1 for complete list); an executed transfer agreement is required in these special cases. Refusal of a research subject participant to allow for future use of identifiable biospecimens-other than required in the protocol or for appropriate regulatory purposes --will be honored.

# Transmission of Data to Outside Investigators:

Coded samples and data may also be sent to our collaborators for analysis. No samples or data collected on this study will be sent outside NIH without prior IRB approval and fully executed material transfer agreement (MTA).

Collaborators include [name]., MaxCyte, Inc. and [name], CRISPR Therapeutics Director, will receive de-identified excess CD34+ cells to conduct preclinical studies aimed at genetically modifying hematopoietic stem cells as a treatment for sickle cell disease. These studies will be performed in vitro only and will not be returned to patients.

Collaborator include [name], with Novartis Institute for Biomedical Research, will receive the bone marrow and peripheral blood sample from sickle cell patients to demonstrate comparability between the results obtained from processing of healthy volunteer bone marrow hematopoietic stem and progenitor cells obtained from healthy donor bone marrow derived HSPC and those from the sickle cell disease patient bone marrow. They will also get the available mobilized peripheral blood CD34+ samples from [name] for similar comparability studies.

Collaborator, [name], with Bioverativ, may receive the bone marrow and mobilized peripheral blood sample from sickle cell patients for ZFN-editing testing. Bioverativ will be investigating gene expression characteristics of these populations. All data derived by Bioverativ from the NIH-sourced CD34+ stem cells that relates to stem cell editing will be shared with the NIH SCD research teams.

Collaborator, [name], with Editas Medicine, may receive peripheral blood, leukocytes, and CD34+ cells from sickle cell patients. Editas is developing genome editing strategies to use CRISPR/Cas9 to introduce mutations in DNA that are associated with reactivation of fetal hemoglobin or to correct the mutation in the beta-globin gene that causes sickle cell disease.

Collaborator, [name]., with UCLA, may receive CD34 cells to perform gene editing to correct the sickle cell mutation and will assay in both culture and xenografted mice.

7.7 Loss or destruction of data/samples

Should we become aware that a major breech in our plan for tracking and storage of samples has occurred, the IRB will be notified.

7.8 Publication Policy

Given the research mandate of the NIH, subject data including the results of testing and responses to treatment will be entered into an NIH-authorized and controlled research database. Any future research use will occur only after appropriate human subject protection institutional approval such as prospective NIH IRB review and approval or an exemption from the NIH Office of Human Subjects Research Protections (OHSRP). Data will not be sent outside the NIH without IRB notification and an executed MTA or CTA.

7.9 Privacy and Confidentiality

All efforts, within reason, will be made to keep subjects' protected health information (PHI) and private identifiable information (PII) private. Using or sharing ("disclosure") such data must follow federal privacy rules. Under certain circumstances, the United States Office of Human Research Protections (OHRP), and the NIH Intramural Institutional Review Board (IRB), will be

able to inspect and copy confidential study-related records which identify participants by name. Therefore, absolute confidentiality cannot be guaranteed.

# At Participating Site:

For St. Jude Children's Research Hospital, see Appendix II for site-specific protocol changes and activities.

# 8.0 Biostatistical Considerations

# 8.1 Sample size

This is a pilot study of safety of plerixafor mobilization in SCD. This study will accrue a maximum of 15 SCD patients at plerixafor 240  $\mu$ g/kg-and safety will be determined by successful accrual without reaching stopping rules.

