# 8.2 Stopping rules

*Death and life-threatening adverse events*: Drug dosing in further participants will be held pending IRB review, if any subject develops any grade IV or V (death) adverse events (Common Terminology Criteria for Adverse Events [CTCAE] version 4.0 or equivalent, see http://ctep.cancer.gov/reporting/ctc.html) considered possibly or definitely related to plerixafor within 10 days of administration of the drug.

*Non-pain crisis related events:* The allowance of a 20% rate for grade III AEs (attributable to plerixafor) is reasonable, given that 30-40% of participant's experience headaches or GI symptoms after plerixafor and a minority of these adverse events might lead to a grade III AE. Drug dosing in further participants will be held pending IRB review, if stopping rules are met in Table 2. Both pain crisis and acute chest syndrome are considered in a separate set of stopping rules below.

We examined the performance of the stopping rule against a range of true non-pain grade III (or higher) AE probabilities – between 10% and 50%. This range was chosen to span plausible AE rates based on clinical experience. The probability of concluding whether the regimen is unsafe (or safe) was determined by the percentage of 100,000 simulated trials in which the stopping rule boundary was reached (or not reached) for a given AE probability. Each simulated trial involved generating 15 dichotomous (yes/no) AE outcomes with the given AE probability and it was determined if the cumulative count of AEs reached the stopping boundary. The boundary was chosen after considering a range of different possible combinations of sample sizes and stopping boundaries. This boundary was selected because the performance balances a strong probability of stopping the trial when the true AE rate is too high (30% or more) and allowing the trial to continue when the AE rate is relatively low (less than 20%).

Table 2 – Stopping rule: Stop if 2 non-pain grade 3 or higher AEs observed in first 5 individuals, 4 AEs after evaluating 6-10 individuals, or 5 AEs after evaluating 11-15 individuals

True, Unknown AE probability	Probability Conclude Safe	Probability Conclude Unsafe
0.50	0.04	0.96
0.40	0.14	0.86

0.30	0.37	0.63
0.20	0.67	0.33
0.15	0.81	0.19
0.10	0.91	0.09

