*Pain crisis related events*: Pain crisis is excluded from the criteria of grade III, while acute chest syndrome is included as grade III or IV. We anticipate up to a rate of 40% for pain crisis (attributable to plerixafor). This rate reflects that among the patients with SCD that have undergone allogeneic HSCT at our center, approximately 30-35% have chronic pain requiring chronic opioid usage and had frequent hospitalizations for pain at baseline. This prevalence is similar to the sickle cell center in Milwaukee, where 34 of 115 patients had 5-11 hospitalizations per year and 17 patients had  $\geq 12.^{36}$  Additionally, all the patients in our current gene therapy study (14-H-0155) had at least 4-5 days of hospitalization after marrow harvest, indicating that pain induced by the harvest procedure is substantial in all patients. The pain from plerixafor would be expected to be lower. Thus, we define pain crisis for this protocol to be (1) duration of hospitalization for the entire HSC collection (e.g. from plerixafor to discharge) to be more than 4 days due to pain that is considered to be sickle related crisis; or (2) hospitalization for pain crisis after discharge from the initial HSC collection and within 10 days of the final plerixafor dose; or (3) escalation in pain treatment (e.g. from oral to IV narcotics administration or from as needed doses of IV to PCA narcotics)..

Hence drug dosing in further participants will be held pending IRB review, if stopping rules are met in Table 3.

True, Unknown AE	Probability Conclude Safe	Probability Conclude Unsafe
probability		
0.60	0.03	0.97
0.50	0.13	0.87
0.40	0.36	0.64
0.30	0.66	0.34
0.20	0.90	0.10

Table 3 – Stopping rule: Stop if 3 pain AEs (defined above) observed in first 5 individuals, 5 AEs after evaluting 6-10 individuals, or 6 AEs after evaluating 11-15 individuals.

The boundaries for pain AEs were determined in a manner similar to the boundary for grade III AEs. Participants will be dosed sequentially, with no overlap during the 10-day monitoring period, (including hospital admission to clinic visit post-stem cell collection) to allow assessment of adverse events in each participant before proceeding to the next. If stopping rules are met at 240 ug/kg, dose reduction may be proposed at that time.

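### Section 8.1 lets completed accrual settle safety without an estimated AE rate, Section 8 plans no summary of the CD34+ yield in the primary endpoint, and 8.2 assigns acute chest syndrome inconsistently

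*Combined protocol and SAP*

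**What the plan says.** Section 8.1 caps the single cohort at 15 patients and gives the only decision criterion in Section 8: "safety will be determined by successful accrual without reaching stopping rules". Section 8.2 supplies the stopping rules.

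- **Non-pain events (Table 2).** The boundary is 2 in the first 5 patients, 4 in patients 6–10 and 5 in patients 11–15. The tolerated rate is given as "The allowance of a 20% rate for grade III AEs (attributable to plerixafor) is reasonable". The boundary is justified by a "strong probability of stopping the trial when the true AE rate is too high (30% or more". Non-stopping is tabulated as the probability of concluding safe.
- **Pain crisis (Table 3).** The boundary is 3, 5 and 6 over the same patient ranges. The expectation is "We anticipate up to a rate of 40% for pain crisis (attributable to plerixafor".
- **Consequence.** "Drug dosing in further participants will be held pending IRB review, if stopping rules are met in Table 2". Table 3 works the same way. A separate rule holds dosing for any grade IV or V event possibly or definitely related to plerixafor.
- **Acute chest syndrome.** The non-pain paragraph says "Both pain crisis and acute chest syndrome are considered in a separate set of stopping rules below". The pain paragraph says "Pain crisis is excluded from the criteria of grade III, while acute chest syndrome is included as grade III or IV", and its three-part definition of pain crisis does not name acute chest syndrome.

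On yield, the precis makes collection of enough stem cells, with acceptable safety, the primary endpoint. Objective 2.2 asks for CD34+ cells/kg, and Appendix II 7.8 lists safety and efficacy as primary objectives. Section 8 does not mention yield. Section 8.0 of Appendix II adds only a limit of 4 patients at St. Jude.

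**The concern.** A stopping rule says when to pause. It does not estimate a rate. Section 8.1 turns not having paused into the safety conclusion, and nothing in Section 8 reports how many events occurred or how precisely the rate is known. Under 8.1 alone, a trial with no non-pain events and a trial with four could be reported in the same words.

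The yield half of the primary endpoint has no planned answer, and the answer depends on what is counted. Section 6.2 lets NIH add a second dose and collection. Section 6.0 of Appendix II allows St. Jude one of each, whatever the yield. A pooled success proportion that does not say which collections count would mix the two.

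The acute chest syndrome conflict decides which boundary an event counts toward, and therefore which rate it enters.

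**Working it through.** **Inputs.** 15 patients with one yes/no outcome each, as in the 8.2 simulation. Boundaries are 2/4/5 (Table 2) and 3/5/6 (Table 3) for patients 1–5/6–10/11–15.

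**Step 1: reproduce the plan's tables.** Let N(k) be the number of ways to place k events among 15 patients without ever reaching the boundary. Then P(pass) = Σ N(k) p^k (1−p)^(15−k).

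- Table 2: N = 1, 15, 95, 345, 755 for k = 0 to 4. For k = 4, at most 1 event may fall in the first 5 patients and at most 3 in the first 10: [C(10,4) − C(5,4)] + 5 × [C(10,3) − C(5,3)] = 205 + 550 = 755.
- Table 3: N = 1, 15, 105, 445, 1260, 2376 for k = 0 to 5.

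At p = 0.30, Table 2 gives 0.0047 + 0.0305 + 0.0828 + 0.1289 + 0.1209 = 0.368. At p = 0.40, Table 3 gives 0.0005 + 0.0047 + 0.0219 + 0.0620 + 0.1170 + 0.1471 = 0.353.

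| Rate | Table 2 printed | Exact | Table 3 printed | Exact |
|---|---|---|---|---|
| 0.60 | – | – | 0.03 | 0.028 |
| 0.50 | 0.04 | 0.037 | 0.13 | 0.128 |
| 0.40 | 0.14 | 0.143 | 0.36 | 0.353 |
| 0.30 | 0.37 | 0.368 | 0.66 | 0.658 |
| 0.20 | 0.67 | 0.670 | 0.90 | 0.898 |
| 0.15 | 0.81 | 0.807 | – | – |
| 0.10 | 0.91 | 0.912 | – | – |

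All agree within 0.01.

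**Step 2: pass both tables.** The 8.1 criterion needs both. Assuming the two event types are independent, at a true non-pain rate of 30%:

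- pain 20%: 0.368 × 0.898 = 0.33
- pain 30%: 0.368 × 0.658 = 0.24
- pain 40%: 0.368 × 0.353 = 0.13

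The grade IV/V hold lowers these further by an amount the documents do not let one compute.

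**Step 3: what a passing trial may contain.** Exact (Clopper–Pearson) 95% limits are the 0.025 quantile of Beta(x, n−x+1) and the 0.975 quantile of Beta(x+1, n−x). For 0/15 the upper limit is 1 − 0.025^(1/15) = 0.218.

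- Non-pain, fewest: 0/15 = 0%, CI 0–22%
- Non-pain, most: 4/15 = 27%, CI 8–55%
- Pain crisis, most: 5/15 = 33%, CI 12–62%

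**Step 4: effect of ignoring the sequential stopping.** Taking each table alone and treating a hold as the end of the trial, coverage of the nominal 95% interval over all trials stays at 0.961 or more (true rates 1–79.5%). Among passing trials only, the observed rate runs low: on average 19% when the true non-pain rate is 30%, and 27% when the true pain rate is 40%. The intervals are usable but need that note.

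**Step 5: yield.** The background study of hematological malignancies cited in Section 3.0 shows how the definition matters. After one dose, 16/24 = 67% reached 2.0x10e6/kg. Adding the 5 who needed a second dose gives 21/24 = 88%, a difference of 5/24 = 21 points. With 15 patients, a hypothetical 10/15 has an exact 95% CI of 38–88%.

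**Step 6: acute chest syndrome.** Suppose that among the first 5 patients one has a grade III acute chest syndrome and another has a different non-pain grade III event. If acute chest syndrome counts as grade III, Table 2 stands at 2 and dosing is held. If it belongs to the pain rules, Table 2 stands at 1 and is not reached. It then enters Table 3 only if it also meets the pain crisis definition, which does not name it.

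**The case against.** The strongest reply is that nothing is hidden. Table 2 prints the 0.37, 8.2 says the boundary balances two errors, and this is a pilot of at most 15 patients. That stands: the tables are right, and the choice of boundary is a disclosed trade-off. It does not supply an estimate. The DSMB review (9.1), the continuing-review summaries (9.5) and the study report (9.6.4) provide a safety review, but none specifies a rate, an interval or a yield summary.

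Several stronger readings are tempting, and the documents do not support them.

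- *The 37% is the chance of the whole 8.1 verdict.* It is the chance for Table 2 alone. The joint figure is lower (Step 2).
- *The verdict is flawed because it depends on the order of events.* Any sequential boundary has that property.
- *Section 9.0 contradicts 8.2 by collecting all grade 3 and higher events when the allowance is for attributable ones.* Collecting more than a rule counts is ordinary, and 9.3 classes possibly and definitely related events as related. The only looseness is that the Table 2 caption omits attribution.
- *The objective in 2.0, which excludes serious adverse events, invalidates the stopping rules.* It differs in wording from the precis, which asks for acceptable safety. That is not an analytical defect.

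On yield, the values in 6.4 are collection goals, and 6.2 ties the second dose to a minimum set by each protocol. Sufficiency may therefore depend on protocols not seen here. That is a reason to state the definition used. It does not justify leaving yield unanalyzed.

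**Conclusion.** The point holds in three parts.

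1. Meeting the 8.1 criterion shows that no boundary was reached. It does not show an acceptable rate. The same result arises 37% of the time under Table 2, and about 13–33% of the time under both tables, at a non-pain rate that 8.2 calls too high. It is compatible with observed rates of up to 27% (non-pain) and 33% (pain).
2. The yield component of the primary endpoint has no planned summary, and the sites differ in whether a second collection is possible.
3. The two statements on acute chest syndrome in 8.2 conflict.

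The figures assume 15 evaluable patients, one yes/no outcome per patient, a 95% confidence level (Section 8 states none) and, for the joint range, independence of the two event types. Section 8.1 gives 15 as a maximum, and the documents do not state the final number. The 67% and 88% come from another population and do not size the effect in sickle cell disease. A reader might infer that the trial reached a wrong safety conclusion or that its tables are in error. Neither follows: no results are given, and the tables reproduce.

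This should be corrected, but it calls for no change to the design or conduct.

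**What to change.** Analysis and reporting only.

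1. **Safety.** Keep the 8.1 criterion and report whether it was met, in the words *no stopping boundary reached*. Add per-patient rates of non-pain grade 3 or higher AEs and of pain crisis, with exact 95% CIs on the number treated and a note that the intervals ignore sequential stopping. For the rate that matches the 20% allowance, use plerixafor-related events as classified in 9.3. Show all collected grade 3 or higher non-pain events alongside.
2. **Yield.** Report first-collection CD34+ cells/kg at both sites: median, range, and the proportions reaching 2.0 and 1.5x10e6/kg with exact 95% CIs. Give NIH cumulative yield separately, and blood volume processed if recorded, because 6.4 ties volume to the target. State that the 6.4 values are NIH collection goals, that 6.2 refers to a protocol-specific minimum, and that St. Jude uses 3.0x10e6/kg as its threshold for research excess.
3. **Acute chest syndrome.** Reconcile the two statements in 8.2 and say which count it entered.

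Section 10.3 records that accrual is closed and the study is in data analysis only. Label added analyses post hoc if they were specified after data were seen.

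The cost is a few lines of text, with no change to conduct. The drawbacks are wide intervals and a first-collection success rate that may look lower than the cumulative one.
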